The complex and coordinated relationship between the endocrine regulation of energy metabolism, adipose tissue, and bone homeostasis has been studied extensively (De Paula et al., 2013). Concentrations of hormones, including insulin and amylin, change profoundly in anticipation of, during or after eating (preprandial, prandial, and postprandial responses). These hormones have potential anabolic effects on bone homeostasis, therefore, synergies between endocrine and mechanical effects could alter the bone turnover response to exercise.

The measurement of bone turnover markers, such as procollagen type 1 N-terminal propeptide (P1NP) and CTX, allow to assess the dynamic fluctuations in metabolic activity of bone (Delmas et al., 2006). Prolonged endurance exercise increases CTX (Guillemant et al., 2004; Hermann et al., 2007; Kerschan-Schindl et al., 2009; Maïmoun et al., 2006; Scott et al., 2010) but bone formation markers are largely unresponsive (Guillemant et al., 2004; Hermann et al., 2007; Maimoun et al., 2006; Scott et al., 2010). This suggests that prolonged exercise might result in a transient negative bone remodelling balance and this acute response may be implicated in changes in bone mineral density with repeated exercise over time in some sub-groups. However, the response of bone turnover markers to exercise is highly variable and appears to be modality-, intensity-, age- and sex-specific.

Feeding modulates the metabolic responses to prolonged exercise. The metabolic adaptations to fuel supply when fed and with fasting are well studied, however, there is limited consideration of the effect of these practices on other biological responses to exercise, such as bone metabolism. Fasting attenuates the circadian variation in CTX, a marker of bone resorption, whilst feeding suppresses resting CTX within 1-hour and concentrations are decreased by around 50% after 2–3 hours (Bjarnason et al., 2002; Henriksen et al., 2003; Holst et al., 2007). In contrast, and in line with the response to exercise, bone

formation is largely unresponsive to nutrient ingestion (Bjarnason et al., 2002; Henriksen et al., 2003; Holst et al., 2007). Concentrations of hormones including insulin and parathyroid hormone (PTH) change profoundly across pre-prandial, prandial, and postprandial states. These hormones have potential anabolic effects on bone homeostasis, therefore, synergies between endocrine and mechanical effects could alter the bone turnover response to exercise.

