6.1. Study design

In this proof-of-concept study, sixteen young adult men (age: 28 ± 4) will be recruited in good physical condition. This will be a three-arm randomised cross-over study with a 1-week washout period between visits (**Figure 1**). Participants will be exercised following a 12-hour overnight fast (FAST) and exercised 90 minutes after a meal (FED) to test the temporal sensitivity of the loaded bone to absorbed nutrients. Participants will also attend a breakfast-only arm (without the exercise protocol). The meal will consist of 60% carbohydrate, 25% fat and 15% protein. The exercise will be a downhill running protocol adapted from previous studies in this area (Scott, 2012; Borer, 2019). Counterbalancing measures will be put in place to prevent and minimise order effects.

Participants will undergo a baseline assessment for health history (PAR-Q). Baseline measurements of weight, height, BMI and maximal oxygen uptake as well as baseline bone mineral density and body composition scans of participants will be performed with a dual energy X-ray absorptiometry (DXA) to characterise the study sample.

Figure 1: Study Design

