6.8 Outcome measures and participant involvement at each visit

All participants will be required to attend the Advanced Wellbeing Research Centre (AWRC) on four separate occasions.

At the **familiarisation visit** each participant will give informed consent. Consenting participants will complete a PAR-Q, undergo a $VO_{2\text{max}}$ test, and DXA scan to measure baseline bone mineral density and body composition. Baseline anthropometric measures, including height, weight, and BMI will be taken. Participants will be asked to follow a standardised diet three days prior to their second study visit. Participants will also be asked to refrain from strenuous physical activity during this period and will be asked to record their food and drink consumption in a diet diary.

At the **second visit**, each participant will arrive after a 12-hour overnight fast.

Counterbalancing measures will be used to assign participants to either the FASTED-exercised, FED-exercised or breakfast only conditions. During the FED-exercised or breakfast only arms, a standardised breakfast will be given at 8.30am. Exercise in the FED condition will take place 1.5 hours after breakfast has been administered (10.00am). When in the fasted condition, participants will also begin exercise at 10.00am.

Blood samples will be taken by cannulation for bone turnover marker measurement and hormone measurement at baseline (8.30am), pre-exercise (immediately before exercise), 15 minutes during exercise, 45 minutes (immediately post-exercise) and 2 hours post-exercise. Timings will also be consistent in the breakfast-only arm.

At the **third and fourth visits**, following crossover periods, participants will be assigned to the alternative conditions and study measurements repeated as per second visit.

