6.9 Statistical analysis

Normality will be assumed if Shapiro-Wilk test is not statistically significant ($P > 0.05$). Where data is normally distributed, the data will be presented as mean and standard deviation (SD). Where data were not normally distributed, data will be presented as median and IQR.

Biochemical data will be analysed using a linear, mixed model (LMM), with factors 'condition' and 'time point' as fixed effects and 'participants' as a random, within-group effect. The assumptions of the LMM (homogeneity of variance and normality) will be investigated by examining the distribution of residuals and the pattern of residuals versus fitted values. Where non-normality or non-constant variance are observed, a log transformation will be applied to the data so that the assumptions are satisfied.

Where there is a significant main effect of *Time* but no significant *Condition* x *Time* interaction, each subsequent time point will be compared against 'Baseline' using a pooled mean from the three groups using Dunnett's test. If the *Condition* x *Time* interaction is significant, within each group, each time point will be compared against baseline using a Dunnett's test and groups will be compared to each other at all time points using the Student Newman-Keuls (SNK) test.

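### For CTX, breakfast alone is expected to make the Condition x Time test significant; SNK then tests FED-exercised against breakfast-only at each time point with no adjustment over time, giving about a 14-17% chance of a false exercise effect if each test is run at 5%

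*Combined protocol and SAP*

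**What the plan says.** Section 6.1 describes the design: "This will be a three-arm randomised cross-over study with a 1-week washout period between visits". Section 6.8 sets which conditions are fed: "During the FED-exercised or breakfast only arms, a standardised breakfast will be given at 8.30am". FAST receives no breakfast. Blood is drawn "at baseline (8.30am), pre-exercise (immediately before exercise), 15 minutes during exercise, 45 minutes (immediately post-exercise) and 2 hours post-exercise", and for the control condition "Timings will also be consistent in the breakfast-only arm". So two of the five samples come before any running and three come after it starts.

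Section 5.1 gives the expected meal response: "feeding suppresses resting CTX within 1-hour and concentrations are decreased by around 50% after 2–3 hours". The same section describes bone formation as largely unaffected by eating.

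Section 6.9 fits a linear mixed model with condition and time point as fixed effects and participant as a random effect. If the Condition x Time interaction is significant, two sets of tests follow. For changes over time, "within each group, each time point will be compared against baseline using a Dunnett's test". For differences between conditions, "groups will be compared to each other at all time points using the Student Newman-Keuls (SNK) test". No adjustment across time points is stated for the second set. No significance level is stated for the mixed model, Dunnett or SNK tests; the only 0.05 in section 6.9 belongs to the Shapiro-Wilk check.

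Section 6.2 defines the primary outcome as the FAST versus FED difference in CTX change from pre-exercise to 2 hours post-exercise, powered at a two-sided 2.5% level.

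**The concern.** Requiring a significant interaction first protects the later tests only if the interaction is unlikely when the effect of interest is absent. Here the effect of interest in FED-exercised versus breakfast-only is exercise, but the interaction can be produced by breakfast. An interaction that appears because two conditions were fed and one was not says nothing about exercise, yet it releases the exercise comparisons.

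SNK then works within one time point. Once FAST stands apart from the two fed conditions, the step-down reaches FED-exercised versus breakfast-only as a two-mean range at the full level, and this is repeated at each sample. The within-condition tests get Dunnett's adjustment over time; the between-condition tests get none.

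What is at stake is a claim that exercise changes CTX in the fed state. Breakfast-only is the sole condition without exercise, so this is the comparison that isolates exercise, and the claim could rest on whichever sample happened to cross the threshold.

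**Working it through.** **1. The plan's own figure.** Section 6.2 gives a difference of 0.168 µg/l, SD 0.2 µg/l, 2.5% two-sided and 80% power. A paired normal approximation gives n = (0.2 × 3.083 / 0.168)² = 13.47, so 14, plus 2 for withdrawals = 16. The stated 16 is reproduced if 0.2 is the SD of the paired difference in change. That difference combines four measurements, so its variance is 4σ² and the residual SD is σ = 0.2 / 2 = 0.10 µg/l. The documents do not say which SD is meant, so this is an inference.

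**2. Size of the meal effect.** The implied baseline is 0.168 / 0.30 = 0.56 µg/l. A 50% fall is 0.28 µg/l.

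**3. Does SNK step down?** With 14 completers and 15 cells the residual degrees of freedom are 13 × 14 = 182, and the 5% studentized-range values are 3.34 (three means) and 2.79 (two means). The standard error of a cell mean is 0.10 / √14 = 0.0267. A gap of 0.28 gives 0.28 / 0.0267 = 10.5, far above 3.34. After the meal, FAST therefore separates and the two fed conditions are compared against 2.79, which is √2 × 1.97: an ordinary 5% t-test.

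**4. Independent-tests benchmark at 5%.**
- Three samples after running starts: 1 - 0.95³ = 14.3%
- Four samples after breakfast: 1 - 0.95⁴ = 18.5%
- All five samples: 1 - 0.95⁵ = 22.6%

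At 2.5% over three samples: 1 - 0.975³ = 7.3%.

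**5. Simulation of the section 6.9 procedure.** FED-exercised is set equal to breakfast-only throughout (no exercise effect). FAST is higher by 0, 0.17, 0.22, 0.28 and 0.28 µg/l at the five samples for the 50% meal effect, or by 0.168 at each of the four later samples for a 30% effect. The within-visit correlation ρ is an assumption, and the SD of one measurement is 0.10 / √(1 - ρ). There are 14 completers and each test is at 5%.

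| Meal effect | ρ | Interaction significant | False difference, any of 5 samples | False difference, 3 samples after start |
|---|---|---|---|---|
| 50% | 0 | 100% | 20.0% | 13.8% |
| 50% | 0.3 | 99.9% | 23.4% | 16.9% |
| 50% | 0.5 | 98.7% | 22.4% | 16.9% |
| 50% | 0.7 | 82.1% | 18.4% | 15.0% |
| 30% | 0 | 91.9% | 19.5% | 13.7% |
| 30% | 0.5 | 54.3% | 15.0% | 11.3% |
| 30% | 0.7 | 14.6% | 4.6% | 3.6% |

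At the 8.30am sample, with ρ = 0, the false rate is about 2.3% rather than 5%, because no meal effect exists yet and the three-mean range still protects.

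**6. Sensitivity.**
- SNK at 2.5%: about 7-10% over the three samples.
- A separate error term at each time point instead of the pooled one: 12.7-14.2% for the 50% effect with ρ up to 0.5.
- 0.2 read as the SD of a single measurement: the interaction is significant in about 43-82% of trials, and the three-sample rate is about 9-15%.
- No meal effect, ρ = 0: the interaction is significant in about 5% of trials, and the three-sample rate is about 2%.

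**7. After adjustment.** A paired analysis of FED-exercised minus breakfast-only changes, adjusted over the three later samples, gives about 4-5%.

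**The case against.** Much of the case on the other side stands, and it sets the limits of the point.

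- **Size.** A reader might infer a false exercise effect of about 20%, four times nominal. That counts the 8.30am and pre-exercise samples. Both precede running, so a difference there cannot be read as an exercise effect. Only three samples count.
- **Level.** The 5% per test is assumed. The only level the documents attach to a comparison is the 2.5% in section 6.2, and at that level the rate is about 7-10%.
- **Certainty of the interaction.** A reader might infer that the interaction must be significant. It is likely when the meal effect is near 50% and the data are as precise as the sample-size calculation implies. With a smaller effect and strong within-visit correlation it often is not, and the rate can then fall below 5%.
- **Primary outcome.** A reader might infer that the primary result is compromised. The documents do not support that: FAST versus FED change from pre-exercise to 2 hours is a single, different contrast.
- **Other markers.** The same rule covers every biochemical measure, which invites the inference that all are equally affected. Section 5.1 expects little P1NP response to feeding, so the interaction test keeps its protective role there. Insulin, glucose and cortisol were not examined.
- **SNK itself.** With three conditions SNK does control error within one time point. The inflation comes only from repeating it over time.

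None of this supplies an adjustment over time for FED-exercised versus breakfast-only. That this is a proof-of-concept study with a different primary contrast lowers the severity but does not remove the point.

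**Conclusion.** The point holds for CTX in the secondary FED-exercised versus breakfast-only comparison. By the plan's own background, the preliminary interaction test offers little protection, and nothing else adjusts across time. With 5% per test, 14 completers and a meal effect near 50%, the chance of at least one false exercise effect over the three samples after running starts is about 14-17%, roughly three times the assumed level. It is about 10-12% with a smaller meal effect or noisier data (lower still in the extreme setting shown), and about 7-10% at 2.5% per test. The figures rest on the assumed test level, the assumed within-visit correlation and the reading of the 0.2 µg/l SD. This should be corrected before analysis; it does not undermine the primary contrast.

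**What to change.** Amend section 6.9 as follows.

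1. State the primary analysis as the single FAST versus FED comparison of CTX change from pre-exercise to 2 hours post-exercise, as section 6.2 defines it, with its significance level.
2. Replace SNK at all time points with model contrasts of change from pre-exercise at the three samples after exercise starts: FED-exercised minus breakfast-only, and the other condition pairs, all as secondary.
3. Adjust each contrast over those three samples by Holm or multivariate t at a stated level, and report simultaneous confidence intervals. Multivariate t gives matching tests and intervals directly.
4. Do not make these contrasts conditional on the interaction p-value.
5. Let the model carry a visit-within-participant effect, or analyse paired changes. With a participant effect alone, within-visit correlation stays in the residual and the standard error of a change contrast is too large by about 1 / √(1 - ρ), for example 1.41 at ρ = 0.5.

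The cost is SAP wording and wider intervals for the secondary comparisons. With a Bonferroni bound over three samples, the critical value at 182 degrees of freedom rises from 1.97 to at most 2.42 (2.42 / 1.97 = 1.23, or 1.22 before rounding), so up to about 22% wider. For a paired analysis of 14 participants (13 degrees of freedom) it rises from 2.16 to at most 2.75, about 27% wider. No extra participants or samples are needed.

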6.2 Power calculation

The primary outcome of this study is the difference in change in CTX concentration between the pre-exercise and 2-hour post-exercise timepoints between the fasted-exercised and fed-exercised arms.

Based on changes in CTX from a previous study (Scott et al., 2012), we designated 30% as a minimally significant difference and that 30% would be approximately 0.168 µg/l. We calculated a standard deviation of 0.2 µg/l based on results from our previous studies with serial measurements of CTX. To achieve 80% power for demonstrating this mean difference as statistically significant at the 2.5% two-sided level requires a total of 16 participants (including 2 additional participants for withdrawals). This sample size is in line with that of other studies in this area.

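### Section 6.9 leaves day-to-day CTX variation in the between-condition comparisons at each time point, although a fasting 8.30am value that could adjust for it is collected at every visit

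*Combined protocol and SAP*

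**What the plan says.** Section 6.8 has participants come to the first experimental visit fasted ("each participant will arrive after a 12-hour overnight fast") and repeats the procedures at the other two. Blood is drawn "at baseline (8.30am), pre-exercise (immediately before exercise), 15 minutes during exercise", at the end of exercise and 2 hours later, with matching times in the breakfast-only arm. The table in 6.8.2 lists CTX at all five times.

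Section 6.9 analyses the biochemical data with a linear mixed model: condition and time point are fixed and participant is the only random effect. The 8.30am value has two roles. It is one level of time point, and it is the reference for Dunnett comparisons over time. When Condition x Time is significant, "groups will be compared to each other at all time points using the Student Newman-Keuls (SNK) test". No baseline covariate and no visit-level term is stated.

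The primary outcome in 6.2 is a different quantity: "the difference in change in CTX concentration between the pre-exercise and 2-hour post-exercise timepoints", compared between the fasted-exercised and fed-exercised arms.

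**The concern.** A participant random effect removes stable differences between people. It does not remove the tendency of one person's CTX to run high or low on a given day. In a crossover each condition falls on its own day, so that variation goes directly into a comparison of condition levels at a time point. Having the 8.30am value in the model as an outcome does not correct this: each condition has its own free mean at 8.30am, and nothing ties a visit's later values to that visit's 8.30am value.

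The pre-exercise sample cannot serve as the covariate, because in the two breakfast conditions it follows the meal and so already carries the effect of condition. The 8.30am sample is the only candidate taken in the same state in all three arms.

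Testing conditions against each other at all time points also includes 8.30am, when nothing has yet been done differently. A significant result there could only be chance and would be awkward to report. At stake is precision in a small trial, using data that will be collected anyway.

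**Working it through.** **Inputs.** From 6.2: difference 0.168 µg/l, SD 0.2 µg/l, 80% power, 2.5% two-sided, 16 participants of whom 2 allow for withdrawals. From 6.1: three conditions per participant. Assumed: the visit-level correlation ρ between the 8.30am value and a later value at the same visit, after removing the participant's own level. The documents do not give it; 0 to 0.7 is shown.

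**The plan's own figure.** Treating 0.2 as the SD of a paired difference, with a normal approximation:

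n = (0.2 × (2.2414 + 0.8416) / 0.168)² = 13.47, rounded up to 14; 14 + 2 = 16.

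This reproduces the stated size, so 14 evaluable participants are used below.

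**Comparison of levels at one time point.** Write a CTX value as condition-by-time mean + participant effect p + visit-day effect v + sample error e. In a difference between two conditions at the same time point, p cancels. The two visit effects belong to different days and do not cancel. The variance per participant is 2(σv² + σe²), and ρ = σv² / (σv² + σe²).

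**With the 8.30am covariate.** The SD is multiplied by √(1 − ρ²). The cost of estimating the slope: 14 × 3 = 42 values at a time point leave 42 − 14 − 2 = 26 residual degrees of freedom. The expected variance inflation is 1 + 1/(26 − 2) = 1.042, or √1.042 = 1.021 on the standard error.

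| ρ (assumed) | √(1 − ρ²) | × 1.021 | SE ratio in simulation (6,000 runs) | Change in SE |
|---|---|---|---|---|
| 0 | 1.000 | 1.02 | 1.02 | +2% |
| 0.3 | 0.954 | 0.97 | 0.97 | −3% |
| 0.5 | 0.866 | 0.88 | 0.88 | −12% |
| 0.7 | 0.714 | 0.73 | 0.73 | −27% |

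Formula and simulation agree. The ratios do not depend on the SD of 0.2.

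Subtracting the 8.30am value is a poorer choice. It multiplies the SD by √(2(1 − ρ)), which is 1.18 at ρ = 0.3, 1.00 at 0.5 and 0.77 at 0.7.

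**The primary outcome.** The change within a visit is (mean at 2 h + p + v + e₂) − (mean pre-exercise + p + v + e₁). Both p and v cancel, leaving only sample error, which the 8.30am value does not predict. In a separate simulation (20,000 runs, 14 participants, three conditions, five times, additive visit shift), the correlation of the 8.30am difference with the difference in change lay between −0.003 and 0.001 for every ρ from 0 to 0.9. Its correlation with the difference in 2-hour level was close to ρ itself. The ρ = 0 row is therefore the relevant one for the primary outcome under an additive shift.

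**The case against.** The strongest reply is that the baseline is already in use. It is a level of time point and the Dunnett reference, and the between-condition tests run only after a significant Condition x Time interaction, whose contrasts include differences from 8.30am. That is correct, and it would be wrong to call the baseline unused. But the comparisons that follow the gate are of unadjusted levels, and those carry the visit variance in full.

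A second reply is that Section 6.8 already limits day-to-day variation through the overnight fast, three days of standardised diet, no strenuous activity and fixed clock times. This also stands. It may put ρ at the low end, where the gain is small.

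A reader might go further and put these reductions into the 6.2 calculation, reading off simulated power of 79%, 87% or 97% against about 76% unadjusted. The documents do not support that. The 0.168 and 0.2 there belong to a within-visit change, in which an additive day shift has already gone. If day effects were proportional to level, cancellation would be incomplete, but a large gain would need large swings. The reference CTX implied by 6.2 is 0.168 / 0.30 = 0.56 µg/l, and the SD per visit is 0.2 / √2 = 0.141. Suppose, for illustration, that CTX changes by 30% of its level within the visit. A correlation of 0.5 then needs a day-to-day SD of 0.5 × 0.141 / 0.30 = 0.24 µg/l, about 42% of the mean. With a 50% change it needs 0.14 µg/l, about 25%. The documents report no such figure. A log transformation, which 6.9 allows when residuals call for it, would turn a proportional shift back into an additive one. The primary gain is uncertain, not excluded.

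A reader might also infer that comparisons against baseline should become descriptive. Nothing here argues for that; they describe the time course and bear on the objectives in Section 4.

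**Conclusion.** The point holds for the between-condition comparisons at the time points after 8.30am. As written, they keep visit-to-visit variation that a measured covariate could partly remove. The standard error would fall by about 3%, 12% or 27% at correlations of 0.3, 0.5 or 0.7, and rise by about 2% at zero. This rests on 14 evaluable participants with complete visits and on an assumed correlation. It also rests on the 8.30am sample preceding the meal. That is the natural reading of baseline, but Section 6.8 gives sample and breakfast the same clock time without stating their order.

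For the primary FAST versus FED contrast in change, little or no gain should be claimed unless day effects are not additive. The covariate also does not stand in for a visit-level random term, which is a separate question about the model's error structure.

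**What to change.** In Section 6.9:

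- Remove 8.30am from the between-condition comparisons.
- For the between-condition comparisons at the four later time points, enter each visit's 8.30am value as two covariates: the participant's mean over the three visits, and the visit's deviation from that mean. With complete data the deviation does the work; the mean term keeps between-person differences out of its slope.
- Keep the planned Dunnett comparisons against baseline. They need 8.30am as a level of time point, so the covariate model is a second fit to the later time points.
- Attach no power gain to the primary outcome on this account.
- In Section 6.8, state the order of the 8.30am sample and the breakfast, since the adjustment depends on it.

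The cost is a few lines of SAP wording and one or two degrees of freedom, about 2% on the standard error if the covariate proves useless. No further samples are needed. It should be settled before the data are seen.
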